7.4 Reporting Procedures

The PI will be responsible to monitor the overall study, including both research data and clinical procedures. The PI will be responsible for reporting all adverse events to the necessary parties. The investigator and team will meet weekly to review safety concerns, unanticipated problems or adverse events. All adverse events will be reported to the IRB and the committee overseeing the study within 30 days.

7.5 Follow-up for Adverse Events

In the case of an adverse event, participants will be referred to the neighboring UNC hospital. All follow-up visits and procedures regarding adverse events will be handled through the UNC Hospital system. A representative from our team will call the participant one week after the adverse event occurs to check-in.

7.6 Safety Monitoring

The investigator will monitor subject data, without a safety monitoring board. The investigator and team will meet weekly to review safety concerns, unanticipated problems or adverse events.

8. INTERVENTION DISCONTINUATION

Subjects may withdraw from the trial at any time at their own request, or they may be withdrawn at any time at the discretion of the Investigator or Sponsor for safety, behavioral or administrative reasons.

The Investigator may discontinue a subject if, in the opinion of the Investigator, the subject is no longer a suitable candidate for the study. Possible reasons for the

discontinuation of a subject are including but not limited to: adverse event, protocol deviation, missed appointment, subject no longer meets the eligibility criteria.

Patients may be removed from the study due to an allergic reaction to a mouth rinse or due to failure or inability to comply with study procedures.

If a patient suffers from xerostomia/dry mouth, such that s/he cannot produce the baseline salivary sample volume or the immediate, 15 minute and 30 minute post-rinse saliva volumes, s/he will be removed from the study with a parking voucher, but without a gift card and will be replaced. If a patient suffers from dry mouth, such that s/he cannot produce salivary sample volumes needed for later time points (45 minutes or 60 minutes post-rinse) but s/he produced sufficient baseline, immediate, 15 minute and 30 minute post-rinse samples, s/he will still be compensated with a gift card and parking vouchers, and will remain in the study. Missing or deficient salivary samples will be noted in CDART.

9. STATISTICAL CONSIDERATIONS

9.1 General Design Issues

A double-blinded, randomized controlled trial was chosen as the study design. It allows us to collect human based data on the effects of commercially available mouth rinses on salivary infectivity and viral load. A crossover study was not pursued because the repeated use of different mouth rinses is likely to confound the results. A 1-hour time-course was chosen to correspond with the average length of most dental procedures. Fifteen minute intervals were chosen to evaluate viral kinetics over time, and to see when infectivity rebounds post- mouth rinse.

Statistical Hypothesis

The central hypothesis of this study is that a 60 second antiseptic mouth rinse will effectively reduce viral infectivity (>50%) of SARS-CoV-2 for a minimum of 30 minutes duration.

The secondary hypothesis is that a 60 second mouth rinse will be well tolerated in a clinical care setting by a majority of patients and providers.

Sample Size Considerations

Based on our similar viral load studies evaluating mouth rinse efficacy against SARS-CoV-2 and other enveloped viruses, we used power calculations to estimate effect size and determine sample size as a function of length of mouth rinse time course.¹² With simultaneous comparisons, the sample size n=43 for each mouth rinse can detect the effect size in Cohen's $d = 0.8$, which is between medium and large, under 80% power and 0.016 type-I error rate by Bonferroni correction.¹² To account for 14% of patients having no virus in their saliva and 10% of patients producing insufficient saliva, we plan to enroll 55 participants per arm.

Statistical analysis of our deidentified data will be performed by [name], the statistician on this project.

Primary Outcomes

The analyses will compare viral RNA level (qRT-PCR) and viral infectivity levels between mouth rinse types and across the time course

Data generated from the qRT-PCR assays will be presented as mean standard deviation for normally distributed data and as median [Interquartile range] for non-normally distributed data. P values will be reported as two tailed. Between group comparisons will be performed using a Student's t test or Mann-Whitney U test. Normality will be assessed using the Kolmogorov-Smirnov test, and logistic regression will be performed with robust standard errors.

The viral infectivity analysis will compare infectivity levels between mouth rinse types and across the time course for calculation of the reduction factor (RF). The RF will be calculated as the difference in the quotient of the infection titre before ('control titration') and after the mouth rinse ('remaining virus'). Therefore, the log₁₀ titre and its (double) standard deviation (SD) were calculated as well as the variance of the RF.

Secondary Outcomes

Survey statistical analysis will be conducted by Odum Institute's statistical consultant, [name]. We will use descriptive statistics, frequency counts and means to evaluate feasibility and acceptability of using point-of-care mouth rinses in clinical workflow.

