Subjects will be asked to rinse with an unlabeled/blinded antiviral mouth rinse for 60 seconds and provide 5 mL of saliva prior to the rinse and 2 mL of saliva immediately post-rinse, 15 minutes post-rinse, 30 minutes post-rinse, 45 minutes post-rinse, and 60 minutes post-rinse. Subjects will also be asked to complete a short survey about the rinsing experience. Subjects will be onsite for a 70-90 minute, single visit appointment.

Sample Size and Population

We will enroll 84 COVID+ subjects per mouth rinse, with 3 mouth rinses (including a water control), requiring us to enroll 252 COVID+ patients. Patients will be

randomized to their selected mouth rinse assignment. These patients will have already had a confirmed COVID+ test within 10 days prior to enrollment. In addition to having a COVID+ test, patients will need to be at least 18 years of age and at most 65 years of age and in good oral health without any known allergies or reactions to the ingredients of the mouth rinses. Patients who are pregnant/ nursing/lactating, have a cognitive or developmental disability, have an active oral herpes flare up, have any oral viral infection and/or flare up, have significant mucosal tears, growths or damage to their mouth, have uncontrolled severe periodontal disease with bleeding gums, or have xerostomia will be excluded from the study. There is no exclusion criteria based on gender or race.

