Participants will be asked to give a baseline salivary sample (5ml over 5 minutes) and then asked to rinse with an unlabeled (blinded) antiseptic mouth rinse for 60 seconds according to the table below. The rinses and control will be similar in appearance visually, such that a double-blind can be maintained. The research assistant ([name]) will be the sole unblinded staff member who will perform randomization and communicate the subject's group assignment to blinded study staff, in advance of the visit based on the block randomization schedule. The unblinded staff member will set-up the rinses for the participants appointment minimizing the possibility of study staff being able to identify the blinded rinses. In the instance that [name] is unavailable, [name] or [name] will perform randomization and set-up the rinses. Blind will be strictly maintained except in the case of medical emergency requiring reveal of an individual's rinse identity. The product group key will be provided to the analyzing statistician at the conclusion of the clinical study.

mouth rinse*	Number of participants (sample size)	Group
26.9% ethanol plus essential oils	84	Experimental
0.1% Cetylpyridinium Chloride	84	Experimental
Sterile water	84	Control

**All mouth rinses are commercially available in the USA, routinely used in clinical settings, and will be used in an on-label manner.*

After the participant expectorates the mouth rinse, research staff will collect another salivary sample (T_0 , 2 mL over 5 minutes). During a 10 minute recuperation period, the study participants will answer demographics survey questions and questions regarding the taste, color, flavor and general acceptability of using the mouth rinse as part of routine dental and medical visits as well as in social settings. At 15 minutes post-rinse, the participant will be asked to provide an additional saliva sample (2 mL over 5 minutes), followed by another 10 minute recuperation period. This sequence will be repeated for at

the 30, 45 and 60-minute time points post rinse. At 60 minutes, the study participant will give their final salivary sample (2 mL over 5 min), and study participation will conclude.

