6.2.5 Completion/Final Evaluation

This study requires only one 70-90 minute, single visit appointment. After consenting and randomization, subjects will be asked to rinse with an unlabeled/blinded antiviral mouth rinse for 60 seconds and provide 5 mL of saliva prior to the rinse and 2 mL of saliva immediately post-rinse, 15 minutes post-rinse, 30 minutes post-rinse, 45 minutes post-

rinse, and 60 minutes post-rinse. Subjects will also be asked to complete a short survey about the rinsing experience.

Subjects may withdraw from the trial at any time at their own request, or they may be withdrawn at any time at the discretion of the Investigator or Sponsor for safety, behavioral or administrative reasons.

The Investigator may discontinue a subject if, in the opinion of the Investigator, the subject is no longer a suitable candidate for the study. Possible reasons for the discontinuation of a subject are including but not limited to: adverse event, protocol deviation, missed appointment, subject no longer meets the eligibility criteria.

Patients may be removed from the study due to an allergic reaction to a mouth rinse or due to failure or inability to comply with study procedures.

If a patient suffers from severe xerostomia/dry mouth, such that s/he cannot produce the baseline salivary sample volume or the immediate, 15 minute and 30 minute post-rinse saliva volumes, s/he will be removed from the study with a parking voucher, but without a gift card and will be replaced. If a patient suffers from dry mouth, such that s/he cannot produce salivary sample volumes needed for later time points (45 minutes or 60 minutes post-rinse) but s/he produced sufficient baseline, immediate, 15 minute and 30 minute post-rinse samples, s/he will still be compensated with a gift card and parking vouchers, and will remain in the study. Missing or deficient salivary samples will be noted in CDART. Severe xerostomia is an exclusion criteria during screening, yet we anticipate that some individuals may not know that they have severe xerostomia until they are participating in the study visit and then need to discontinue due to reduced salivary flow, as described.

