9.2 Sample Size and Randomization

Based on similar viral infectivity studies evaluating antiviral mouth rinse efficacy, we were able to run power calculations to estimate effect size and determine sample size as a function of length of mouth rinse time course. The sample size is justified by a paired t-test on outcomes between time points. With simultaneous comparisons, the sample size n=43 for each mouth rinse can detect the effect size in Cohen's $d = 0.8$ at 30 minutes, which is between medium and large, under 80% power and 0.016 type-I error rate by Bonferroni correction.¹² To account for 14% of patients having no virus in their saliva and 10% of patients producing insufficient saliva, we plan to enroll 55 participants per arm.

The statistical consultant on this project will create a block randomization tool for the study staff; the unblinded staff member will randomize a participant once enrollment compliance has been confirmed and consent has been given. The participant's group assignment will then be communicated to the blinded study staff. IRB approved study personnel will ask participants screening questions to confirm eligibility for enrollment. After consent and screening, the randomization tool will be used by study staff to assign the subject to a study group.

The researcher responsible for collecting the salivary samples will be blinded to the mouthwash solution, as they will be given a pre-aliquoted mouth rinse in an unlabeled tube to provide to the patient for the rinse.

The PI, Co-I, study coordinators and study personnel who work for GoHealth are authorized to break the blinding based on emergency medical necessity such as if a patient suffers an allergic or adverse reaction to one of the mouth rinses. Though highly unlikely as all mouth rinses are sold commercially at Walgreens and CVS, adverse or allergic reactions are possible. Using the numerical code associated with the participant and mouth rinse syringe, the study personnel responding to the emergency can reference the block randomization schedule to determine the mouth rinse type, to inform the emergency medical workers, poison control or the emergency room what type of mouth rinse product led to the reaction.

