9.4.1 Primary Outcome

The primary objective of this study is to determine the efficacy of antiseptic mouthwashes on reducing SARS-CoV-2 cellular infectivity in COVID+ patient saliva. *We hypothesize that COVID-19+ patients will have a >95% reduction in SARS-CoV-2 viral infectivity following a 60 second oral rinse with an antiseptic mouth rinse and that this reduction will persist for at least 30 minutes.* This primary objective will focus on quantifying SARS-CoV-2 viral infectivity and RNA level using an *in vitro* infectivity assay and quantitative real time PCR. This objective provides urgently needed data to guide healthcare workers on the proper use of specific commercially available mouthwashes capable of reducing SARS-CoV-2 viral infectivity and potentially limiting COVID-19+ transmission.

Outcome assessments will be conducted weeks to months after the study visit, when qRT-PCR and viral infectivity assays are conducted in the COVID core and the [name] lab.

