Power Calculation: Based on our similar viral load studies evaluating mouth rinse efficacy against SARS-COV-2 and other enveloped viruses, we used power calculations to estimate effect size and determine sample size as a function of length of mouth rinse time course.¹² The sample size is justified by a paired t-test on outcomes between time points. With simultaneous comparisons, the sample size n=43 for each mouth rinse can detect the effect size in Cohen's d =0.8, which is between medium and large, under 80% power and 0.016 type-I error rate by Bonferroni correction.¹² To account for 14% of patients having no virus in their saliva, we plan to enroll 55 participants per arm. Analyses will compare viral RNA level (qRT-PCR) and viral infectivity levels between mouth rinse types and across the time course. ANCOVA models will be utilized to look at changes in viral load and infectivity logarithmically before and after treatment.

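### The primary infectivity hypothesis is a reduction above 95% in sections 1.1 and 9.4.1 but above 50% in section 9.1, and the planned reduction factor is tied to neither figure

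*Combined protocol and SAP*

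**What the plan says.** Section 9.4.1 (Primary Outcome), repeating section 1.1, hypothesises that patients "will have a >95% reduction in SARS-CoV-2 viral infectivity following a 60 second oral rinse with an antiseptic mouth rinse" and that the effect lasts at least 30 minutes. Under the Statistical Hypothesis heading in section 9.1, the central hypothesis is that the same 60-second rinse "will effectively reduce viral infectivity (>50%) of SARS-CoV-2 for a minimum of 30 minutes duration". All three statements are current text, and none is marked as superseded or secondary.

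The analysis provisions are:

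- **Reduction factor (sections 9.1 and 9.5).** "The RF will be calculated as the difference in the quotient of the infection titre before" and after the rinse, with its SD and variance. The reference is the pre-rinse titre.
- **Model (section 9.5, power calculation).** "ANCOVA models will be utilized to look at changes in viral load and infectivity logarithmically before and after treatment".
- **Comparisons (sections 9.1 and 9.5).** Infectivity is compared between rinse types and over time. For qRT-PCR there are t or Mann-Whitney tests and a logistic regression with no named outcome.
- **Sample size (section 9.2).** "The sample size is justified by a paired t-test on outcomes between time points", with Cohen's d = 0.8, 80% power and a type I error of 0.016.
- **Control.** Sterile water is the control arm (section 3 and the Précis). The Précis says: "We will enroll 84 COVID+ subjects per mouth rinse, with 3 mouth rinses (including a water control").

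**The concern.** The plan gives two numerical answers to its primary question. A reduction of, say, 80% would meet the hypothesis in section 9.1 and miss the one in sections 1.1 and 9.4.1. No analysis provision sets a null value, confidence limit or success rule at 50% or 95%, and none uses the 30-minute duration as a criterion.

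Section 9.4 says that the study committee which draws the conclusions will know the group assignments and will evaluate the data after the statistician's analyses. With two thresholds on file and no rule, the figure that a result is judged against could be chosen once the result is known. Section 1.1 intends the findings to guide healthcare workers' use of these products, so a claim of a given percentage reduction needs an analysis that supports that percentage.

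**Working it through.** **1. The plan's own figure.** Section 9.2 gives 43 evaluable per rinse for d = 0.8, 80% power and 0.016. A paired t-test on those inputs, two-sided, needs 20 pairs (power 81%), and 43 pairs give 99.6%. So 43 does not reproduce from the test named. The step to 55 enrolled does follow, within rounding: 43 / (0.86 × 0.90) = 55.6. For the present point, what matters is that d = 0.8 is set against a null of no change. Neither 50% nor 95% enters the calculation.

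**2. Thresholds on the log scale.** The limit is −log10(1 − reduction).

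- Above 50%: −log10(0.50) = 0.301 log10, a 2-fold fall.
- Above 95%: −log10(0.05) = 1.301 log10, a 20-fold fall.
- Difference: 1.0 log10.

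**3. Inputs for an illustration.**

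- SD of log10 change: not given in the documents. Assumed 1.0, range 0.75 to 1.5.
- True reduction: 80%, chosen for illustration. −log10(0.20) = 0.699 log10.
- Error rate: 0.016, taken as two-sided, at one time point.
- Evaluable per arm: the documents conflict. The Précis and section 3 enrol 84, which gives 84 × 0.86 × 0.90 = 65. Sections 2.2, 9.1, 9.2 and 9.5 plan 55 enrolled for 43 evaluable. Both are shown.

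**4. What a significant test against zero shows.** The confidence half-width is h = t(0.992; n − 1) × SD / √n.

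- n = 65, SD 1.0: 2.475 / 8.062 = 0.307 log10.
- n = 43, SD 1.0: 2.510 / 6.557 = 0.383 log10.

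With 43 evaluable, an observed mean reduction of 1 − 10^(−0.383) = 59% is just significant against zero. Its lower confidence limit is then a reduction of about 0%, so it establishes neither threshold.

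**5. Observed reduction needed for the lower limit to pass.** This is 1 − 10^−(threshold + h). Ranges are for SD 0.75 to 1.5.

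| Evaluable per arm | To claim >50% | To claim >95% |
|---|---|---|
| 65 | 75.3% (70.6% to 82.7%) | 97.5% (97.1% to 98.3%) |
| 43 | 79.3% (74.2% to 86.7%) | 97.9% (97.4% to 98.7%) |

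**6. Probability of each conclusion if the true within-arm reduction is 80%.** Noncentral t with noncentrality (0.699 − threshold) × √n / SD. For the 50% threshold and SD 1.0 this is 0.398 × 8.062 = 3.21 with n = 65, and 0.398 × 6.557 = 2.61 with n = 43.

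| Evaluable per arm | Significant against zero | Lower limit >50% | Lower limit >95% |
|---|---|---|---|
| 65 | 99.9% (100% to 90%) | 77% (96% to 38%) | below 0.001% |
| 43 | 98% (100% to 71%) | 54% (83% to 23%) | below 0.001% |

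The same data would almost always be significant, would often support above 50%, and would practically never support above 95%.

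**7. Requiring 0, 15 and 30 minutes all to pass.** Simulation with n = 65, SD 1.0, a true 80% reduction at each time and assumed correlation 0.3 to 0.8. The chance of showing above 50% at all three is 51% to 65% at two-sided 0.016, and 72% to 80% at two-sided 0.05. When every time must pass, the all-must-pass rule itself controls the error across times, so a Bonferroni correction over those times is an unneeded second penalty.

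**The case against.** **The reference exists.** A reader might infer that the plan leaves the percentage reduction with no reference at all. The documents do not support that. Sections 9.1 and 9.5 define the only infectivity reduction measure from the titres before and after the rinse, the hypothesis speaks of a reduction following the rinse, and the ANCOVA concerns change before and after treatment. The natural reading is within patient, against pre-rinse. The gap that remains is narrower. The reduction factor is not linked to either threshold. Water is covered only by the general comparison between rinse types, with no contrast of the reduction specified.

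**The hypotheses are nested.** Any reduction above 95% also exceeds 50%, so the statements conflict only for results between the two. That is correct and limits the problem to that interval.

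**The percentages may be expectations.** Sections 1.1 and 9.4.1 can be read as a hoped-for result, not a test criterion. Section 9.1, however, labels its figure the statistical and central hypothesis, and section 9.4.1 is the definition of the primary outcome. If the figures are descriptive, the plan must say so and still give one figure.

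**The illustration rests on assumptions.** The SD and the 80% are assumed, and 0.016 appears only in the sample-size statements; two-tailed reporting is stated only for qRT-PCR. The probabilities move with these inputs. The contradiction does not depend on them.

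**Conclusion.** The point stands and should be corrected before the results are analysed. The primary infectivity hypothesis has two values 1.0 log10 apart, and no planned analysis is aimed at either. A result between 50% and 95% confirms one statement and fails the other. The documents do not show which figure is intended, and it would go too far to infer that either one is the error.

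For a true 80% reduction at one time point, the chance of supporting above 50% is 77% (96% to 38%) with 65 evaluable, or 54% (83% to 23%) with 43. These figures assume an SD of log10 change of 1.0 (0.75 to 1.5), two-sided 0.016 and normally distributed log10 change. The last assumption is fragile: an effective rinse can leave samples with no plaques, and their log10 titre is undefined until a detection-limit value is set.

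**What to change.** 1. State one threshold in sections 1.1, 9.1 and 9.4.1. The sponsor chooses which.
2. Say that it applies to the reduction factor, expressed as mean log10 reduction from the pre-rinse titre, and name the time points through 30 minutes at which it must hold.
3. Choose one of two uses. Either claim the threshold only when the lower confidence limit of the mean log10 reduction exceeds it, or label it a descriptive target and report the estimate with its confidence interval. In neither case read a p-value against zero as support for the threshold.
4. Report the baseline-adjusted difference from water, using the ANCOVA already planned.
5. If all times through 30 minutes must pass, drop any correction across those times. Justify any remaining correction by the number of active rinses.
6. State the value assigned to samples with no plaques.
7. Reconcile 84 with 55 enrolled per arm, because the precision of any threshold claim depends on it.

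The cost is wording in three sections and a decision rule built on quantities already planned, with no new data. The downside is a stricter bar than a test against zero: about 75% observed to claim 50%, or about 97.5% to claim 95%, with 65 evaluable and SD 1.0. The descriptive-target option avoids that cost but gives up the formal claim.
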